8. RESEARCH METHODS

8.1. Study Design

This study is a multi-center, prospective, Non-interventional (NI) Study evaluating the safety and efficacy of CFDA approved sunitinib in Chinese patients with progressive, unresectable, advanced or metastatic well-differentiated, pancreatic neuroendocrine tumors.

Approximately 100 adults with progressive advanced or metastatic well-differentiated unresectable pancreatic neuroendocrine tumors in China hospitals are the target population. Receipt of any previous systemic therapies is not an exclusion criteria. Each subject will be followed up overall survival (OS) time or the date of withdrawal and subjects who remain alive after study completion will have their OS time censored on the last date known to be alive. The dosage of sunitinib is based on individual safety and tolerability in daily clinical practice. Subjects will be treated until disease progress, unacceptable toxicity, withdrawal of subject consent, other withdrawal criteria are met. Subjects with evidence of disease progression may continue on treatment if judged to have clinical benefit. After discontinuation of treatment and mandated 28 day follow-up, subjects will be followed to collect information on further antineoplastic therapy and the time to death as appropriate or until the subjects withdraw their informed consents during the study period. Subjects who

remain alive after study completion will have their OS time censored on the last date known to be alive.

The NI study will capture observations that will be used for evaluating the safety profile of sunitinib, including: subject demographics, medical history and medications. Safety assessments, treatment data and any other laboratory examination results, which were done according to routine clinical practice, will be collected at all visits.

Concomitant medication will be recorded in the case report form.

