8.2.2. Duration of Subject Participation

The frequency of the NI study visits may be conducted following the local medical advice and it is usually once in 1 or 2 months. In the post-treatment follow-up visit, in the event a subject is unable to return to the clinic for the visit, telephone contact with the subject to assess adverse events and concomitant medications and treatments is expected and is to be conducted at least 28 calendar (+10 days). If the subject withdraws from the study, and also withdraws consent for disclosure of future information, no further evaluations should be performed, and no additional data should be collected. The sponsor may retain and continue to use any data collected before such withdrawal of consent. All subjects who don't withdraw from the study will be followed for survival status (if permitted).

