8.3. Variables

This study will collect and analyze the safety and efficacy data from approximately 100 eligible subjects from the time of first subject first visit to the time the study is closed. Since this is primarily an observational study, there are no patient visits specified by virtue of this protocol.

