8.3.1. Baseline Data Collection (Day 0)

The baseline data must be performed prior to the start of sunitinib treatment :

- For the subjects who haven't taken sunitinib and will accept sunitinib therapy, they (or a legally acceptable representative) sign on current Institutional Review Board (IRB)/Independent Ethics Committee (IEC) approved informed consent document.
- Demographic data:
 - Date of birth, height, weight, race.
- Medical history:
 - Cancer history treatment, tumor Ki-67 index(assessment based on previous tumor biopsy results or previous surgical resections to be provided.), response to treatment, ongoing symptoms/events.
- Medication history:

- History of other disease processes (active or resolved), concomitant illnesses and treatments.
- Physical examination:
 - Examination of major body systems, such as general appearance, throat, neck, thyroid, lungs, heart, breasts, abdomen, musculoskeletal, extremities, skin, lymph nodes, neurological, others, ECOG performance status, body weight, height, and vital signs (eg, temperature, blood pressure, and heart rate).
- Hematology and blood chemistry (see [ANNEX 3](#) for laboratory tests):
 - Haematologic: hemoglobin, platelet count, white blood cell count, neutrophile granulocyte count.
 - Blood chemistry: total bilirubin, ALT (Alanine Transaminase), AST (Aspartate Transaminase), alkaline phosphatase, GGT (Gamma-Glutamyl Transferase), total protein, albumin, BUN (Blood Urea Nitrogen), creatinine, uric acid, glucose, hypocalcemia, hyponatremia, hypophosphatemia, hypokalemia.
- 12-lead ECG.
- If applicable, tumor imaging should be performed as appropriate within current clinical practice:
 - CT scans/MRI of chest, abdomen, pelvis, brain and bone scan, in addition to any other applicable sites of disease.

For the subjects who have already taken sunitinib within the past 6 months (26 weeks) and will continue sunitinib therapy, these key element baseline data, such as demographic data, medical history, medication history, physical examination, 12 lead Electrocardiogram (ECG), hematology and blood chemistry, tumor imaging, will be collected prior to their sunitinib treatment after the subject or their legal representative has provided informed consent.

8.3.2. Treatment and Efficacy Data Collection (From First Dosage to Last Dosage of Sunitinib)

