For the subjects who have already taken sunitinib within the past 6 months (26 weeks) and will continue sunitinib therapy, they (or a legally acceptable representative) sign on current Institutional Review Board (IRB)/Independent Ethics Committee (IEC) approved informed consent document on the day that they decide enrollment this study.

- Administration of sunitinib:
 - Dose reduction or escalation for any reason.
- Tumor imaging, if applicable:

- CT scans/MRI of chest, abdomen, pelvis, brain and bone scan, in addition to any other applicable sites of disease.
- Concomitant medications and treatments.

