8.3.4. The Post-treatment Follow-up Visit Data Collection

- Physical Examination within 28 days (+10 days) after the end of treatment or study withdrawal, if applicable:
 - examination of major body systems (such as general appearance, throat, neck, thyroid, lungs, heart, breasts, abdomen, musculoskeletal, extremities, skin, lymph nodes, neurological, others), ECOG performance status, body weight, height, and vital signs (eg, temperature, blood pressure, and heart rate).
- Hematology, blood chemistry, thyroid function testing (see [ANNEX 3](#) for laboratory tests) within 28 days (+10 days) after the end of treatment or study withdrawal, if applicable:
 - Haematologic: hemoglobin, platelet count, white blood cell count, neutrophile granulocyte count.
 - Blood chemistry: total bilirubin, ALT (Alanine Transaminase), AST (Aspartate Transaminase), alkaline phosphatase, GGT (Gamma-Glutamyl Transferase), total protein, albumin, BUN (Blood Urea Nitrogen), creatinine, uric acid, glucose, hypocalcemia, hyponatremia, hypophosphatemia, hypokalemia.
- Assessment of adverse events within 28 days (+10 days) after the end of treatment or study withdrawal.

- Recording of concomitant medications and treatments including antineoplastic therapies.

In the event a subject is unable to return to the clinic for the follow-up visit, telephone contact with the subject to assess adverse events and concomitant medications and treatments is expected. If laboratory assessments are needed to follow-up unresolved adverse events, retrieval of assessments performed at a local institution close to the subject is acceptable.

The outcome of adverse events with a date of onset during the study period should be reevaluated. All serious adverse events, and those non-serious adverse events assessed by the investigator as possibly related to study drug should continue to be followed even after subject withdrawal from study. These adverse events should be followed until they resolve or until the investigator assesses them to be “chronic” or “stable.”

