8.3.5. Survival Follow-up

Survival follow-up includes progression-free survival, PFS by clinical judgment and overall survival.

All subjects will be followed for tumor progression (CT/MRI or clinical judgment) and overall survival (OS) time or the date of withdrawal. Subjects who remain alive after study completion will have their OS time censored on the last date known to be alive.

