6.1.1. Progression-Free Survival

Investigator assessed PFS according to RECIST 1.1. PFS is defined as the time from start date to first document of objective tumor progression or death due to any cause, whichever occurs first. PFS (in months) will be calculated as (first event date — start date +1)/30.44.

PFS data will be censored on the date of the last objective tumor assessment on study for subjects who do not have objective tumor progression and who do not die while on study. Patients with documentation of a PFS event after an unacceptably long interval (>17 weeks) since the previous objective disease assessment will be censored at the date of the previous assessment. Patients with no on-study objective disease assessments are censored at the start date unless death occurred within 17 weeks post first dose (in which case the death is an event). Patients with inadequate baseline disease assessment are censored at the start date. Adequate baseline is defined using the following criteria:

- Subjects with target lesions: All target lesions had measurement(s) within the baseline window (200 days) and measurable.
- Subjects with non-target lesions only: All non-target lesions had non missing assessments(s) and at least one of the non-target lesions assessed as non-indeterminate within the baseline window (200 days).

Additionally, subjects who start a new anti-cancer therapy prior to Progressive Disease (PD) will be censored at the date of the last tumor assessment prior to the start of the new therapy.

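### The protocol is inconsistent on whether progression is recorded after sunitinib stops, so both PFS endpoints may lose post-treatment events

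*Protocol*

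**What the plan says.** These parts of the protocol end or omit progression data once sunitinib stops:

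- Section 8.3.2 carries the heading "Treatment and Efficacy Data Collection (From First Dosage to Last Dosage of Sunitinib". Its list includes "Tumor imaging, if applicable", the only imaging item after baseline in the data-collection lists.
- Section 8.1 says that after discontinuation and the 28-day follow-up, "subjects will be followed to collect information on further antineoplastic therapy and the time to death as appropriate". Progression is not named.
- Section 8.2.2 says that subjects who do not "withdraw from the study will be followed for survival status (if permitted").
- Section 8.3.4, the post-treatment visit, lists examination, laboratory tests, adverse events and "Recording of concomitant medications and treatments including antineoplastic therapies". It has no imaging or progression item.

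Section 8.3.5 says otherwise: "All subjects will be followed for tumor progression (CT/MRI or clinical judgment) and overall survival (OS) time or the date of withdrawal". The abstract and SAP 2.1 repeat this.

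On the analysis side, SAP 6.1.1 states that "PFS data will be censored on the date of the last objective tumor assessment on study" for subjects without objective progression or death. An event more than 17 weeks after the previous objective assessment is moved back to that assessment as a censoring. SAP 6.1.2 has parallel rules for PFS by clinical judgment. Both censor subjects who start new anti-cancer therapy before progression.

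**The concern.** Take a subject who stops for toxicity, a reason for discontinuation listed in protocol 9.2, with no progression and no new therapy. By 8.3.5, later routine scans and the investigator's view of progression are recorded. By the heading of 8.3.2 and the descriptions in 8.1, 8.2.2 and 8.3.4, a site could reasonably enter nothing more about the tumour. Protocol 8.7 refers data entry to section 8.3, which contains both rules, and section 8.3 adds that "there are no patient visits specified by virtue of this protocol". No text says which rule takes precedence.

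Both PFS endpoints run from the start of sunitinib to progression or death, with no end at drug stop. If post-treatment assessments are not entered, subjects leave the risk set around the time they stop, which is when their risk of progression may change. That censoring may be informative, and data that were never entered cannot be recovered at analysis. PFS by clinical judgment is equally exposed, because SAP Appendix 1.1 derives it from the investigator tumour-assessment (IOTA) page.

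**Working it through.** **1. The text.** For a subject off drug without progression, 8.3.5, the abstract and SAP 2.1 say progression is followed. The heading of 8.3.2 stops at the last dose, and 8.1, 8.2.2 and 8.3.4 are silent. The last paragraph of 8.3.3 adds to the confusion: for prior users, it lists tumour imaging among data to be collected after their sunitinib treatment.

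**2. What the SAP does if imaging stops at the last dose.**
- No death, or a death more than 17 weeks after the last assessment: censored at that assessment.
- Death within 17 weeks of it: still an event.
- New therapy before progression: censored under either reading, so nothing further is lost.

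**3. Closed-form illustration of the median.** Protocol section 6 gives Phase 3 medians of 11.4 months (sunitinib) and 5.5 months (placebo). Assume exponential times, the first as the on-drug hazard and the second as the post-stop hazard: l = ln2/11.4 = 0.0608 and l2 = ln2/5.5 = 0.1260 per month, a ratio of 2.07. The fraction p stopping before an event is not in the documents; 10%, 20% and 30% are assumed, with stopping hazard g = l·p/(1−p) = 0.0068, 0.0152 and 0.0261.

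With follow-up through stopping, S(t) = exp(−(l+g)t) + g[exp(−l2·t) − exp(−(l+g)t)]/(l+g−l2). Solving S(t) = 0.5 gives 11.05, 10.68 and 10.27 months. Censoring at stop gives 11.4 throughout. The differences are 0.35, 0.72 and 1.13 months.

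If half of those who stop start new therapy, they are censored under both readings. Halving the second term of S(t) gives the off-drug group still at risk, and the Kaplan-Meier hazard is the risk-set average of l and l2. The medians become 11.22, 11.00 and 10.75, so the differences fall to about 0.2, 0.4 and 0.7 months.

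**4. Simulation with the SAP rules.** This used 200,000 subjects, an on-drug median of 11.4 months, a last scan 0–10 weeks before stop, a median post-progression survival of 20 months, 48 months of follow-up and no new therapy. Medians are in months; the first figure has progression followed after stop, the second has imaging ended at the last dose.

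| 12-month stop probability | Hazard unchanged | Doubled | Tripled | Events per 100 |
|---|---|---|---|---|
| 10% | 11.4 / 11.3 | 10.9 / 11.2 | 10.8 / 11.3 | 95–96 / 84 |
| 20% | 11.4 / 11.2 | 10.6 / 11.1 | 10.2 / 11.1 | 95–97 / 75 |
| 30% | 11.4 / 11.0 | 10.2 / 11.0 | 9.6 / 11.0 | 95–98 / 67 |

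The second figure barely moves with the post-stop hazard, so the estimate cannot register what happens off drug. With the hazard unchanged it is slightly too low (0.1–0.4 months), because censoring falls before the stop date.

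**5. Events when half start new therapy.** On a 10-week scan grid, with a small risk of death before progression added, events per 100 are 90–91 against 85, 86 against 75–76, and 81–82 against 67. The loss is about 5 to 15 per 100.

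**6. Protocol 8.7 without the 17-week rule.** Any death on study then counts, so unseen progressions are replaced by later deaths. In the simulation of step 4 the median rises to 11.7–12.6 months. The error there is late event dates rather than censoring.

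**The case against.** Section 8.3 is arranged by period, and its parts can be read as cumulative. On that reading, 8.3.5 is the rule for follow-up: it covers all subjects, names CT/MRI and is repeated twice elsewhere. Section 8.3.4 is one visit at about 28 days, so the absence of imaging there proves little. The censoring rules refer to assessments on study, not on treatment, and no document says the IOTA page closes at the last dose. All of this stands. It shows the likely intention, but does not tell a site that the last-dose limit in the heading of 8.3.2 is to be disregarded.

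A reader might infer that 8.1 and 8.2.2 restrict follow-up to therapy and survival, and so forbid recording progression. Neither section says so; the restriction is by omission.

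A reader might also infer that 10–30% of PFS events vanish, matching the share assumed to stop. That counts every such subject's event as lost. It ignores new-therapy censoring, which applies under either reading, and deaths within 17 weeks, which remain events.

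The median shift is also small beside sampling error. With 85 events, an exponential 95% interval around 11.4 months is 11.4 × exp(±1.96/√85), or 9.2 to 14.1. That limits the priority; it does not remove the ambiguity or the loss of events.

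**Conclusion.** The inconsistency is real. Its effect is conditional on sites applying 8.3.2 and 8.1 rather than 8.3.5. In that case, subjects who stop without progression and start no new therapy are censored at their last on-treatment assessment, and both PFS endpoints reflect mainly on-drug risk. It would go too far to call PFS a purely on-treatment endpoint, since early deaths still count and the on-study wording points the other way.

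The size rests on assumed stop rates and post-stop hazards; the placebo-arm hazard is borrowed for illustration. The median is 0 to about 1 month too high over most of the range. It reaches 1.4 months with a 30% stop probability and a tripled hazard, and there is no upward bias if the hazard is unchanged. About 5 to 15 events per 100 are lost if half of those who stop start new therapy.

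PFS is secondary, the study is non-comparative and no decision rule depends on it. This is a modest-priority internal inconsistency, not a design choice.

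**What to change.** - Align protocol 8.1, 8.2.2, 8.3.2 and 8.3.4 with 8.3.5. State that, for subjects who stop sunitinib without progression, tumour assessments done in routine practice and the investigator's progression status continue to be recorded on the IOTA page after the last dose, until progression, death, withdrawal or study end.
- Leave on-treatment imaging collection as it is. The protocol allows treatment beyond progression, so ending the 8.3.2 item at progression would drop scans it now collects. Adding an item to the 28-day visit alone would miss later progression.
- State in SAP 6.1.1 and 6.1.2 that the on-study period includes post-treatment follow-up.
- Report how many subjects were censored after stopping without progression.

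The cost is wording in both documents and a little extra data entry for subjects who stop without progression. No extra scans or visits are needed, and neither the sample size nor any error rate changes.

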8.3.3. Safety Data Collection (From First Dosage to Last Dosage of Sunitinib)

- Physical examination:
 - examination of major body systems, such as general appearance, throat, neck, thyroid, lungs, heart, breasts, abdomen, musculoskeletal, extremities, skin, lymph nodes, neurological, others, ECOG performance status, body weight, height, and vital signs (eg, temperature, blood pressure, and heart rate).
- All AE and SAE data

Data collection includes:

1. Infections.
2. Cardiac and vascular:
 - 12-lead ECG.
 - MUGA or ECHO for LVEF assessment (if applicable, within current clinical practice).
3. Skin and subcutaneous tissue:
 - The most common skin and subcutaneous tissue related adverse events of interest are rash (includes erythematous, macular, or scaly rash), hand foot syndrome (HFS) or palmoplantar erythrodysesthesia (PPE), dry skin and skin discolouration.
4. Gastrointestinal.
5. Psychiatric and nervous system.
6. Musculoskeletal.
7. Thyroid function (if applicable, within current clinical practice):
 - Thyroid function testing (see [ANNEX 3](#) for laboratory tests).
8. General disorders.
9. Others.

10. laboratory abnormalities:

- Haematologic: hemoglobin, platelet count, white blood cell count, neutrophile granulocyte count.
- Blood chemistry: total bilirubin, ALT (Alanine Transaminase), AST (Aspartate Transaminase), alkaline phosphatase, GGT (Gamma-Glutamyl Transferase), total protein, albumin, BUN (Blood Urea Nitrogen), creatinine, uric acid, glucose, hypocalcemia, hyponatremia, hypophosphatemia, hypokalemia. Urine protein assessment, if applicable (see [ANNEX 3](#) for laboratory tests).

This data will be reported on the appropriate electronic CRF and Adverse Event Monitoring (AEM) forms during treatment with sunitinib.

For the subjects who have already taken sunitinib within the past 6 months (26 weeks) and will continue sunitinib therapy, these key element data, such as demographic data, medical history, medication history, physical examination, 12 lead Electrocardiogram (ECG), hematology and blood chemistry, tumor imaging, will be collected after their sunitinib treatment.

8.3.4. The Post-treatment Follow-up Visit Data Collection

- Physical Examination within 28 days (+10 days) after the end of treatment or study withdrawal, if applicable:
 - examination of major body systems (such as general appearance, throat, neck, thyroid, lungs, heart, breasts, abdomen, musculoskeletal, extremities, skin, lymph nodes, neurological, others), ECOG performance status, body weight, height, and vital signs (eg, temperature, blood pressure, and heart rate).
- Hematology, blood chemistry, thyroid function testing (see [ANNEX 3](#) for laboratory tests) within 28 days (+10 days) after the end of treatment or study withdrawal, if applicable:
 - Haematologic: hemoglobin, platelet count, white blood cell count, neutrophile granulocyte count.
 - Blood chemistry: total bilirubin, ALT (Alanine Transaminase), AST (Aspartate Transaminase), alkaline phosphatase, GGT (Gamma-Glutamyl Transferase), total protein, albumin, BUN (Blood Urea Nitrogen), creatinine, uric acid, glucose, hypocalcemia, hyponatremia, hypophosphatemia, hypokalemia.
- Assessment of adverse events within 28 days (+10 days) after the end of treatment or study withdrawal.

- Recording of concomitant medications and treatments including antineoplastic therapies.

In the event a subject is unable to return to the clinic for the follow-up visit, telephone contact with the subject to assess adverse events and concomitant medications and treatments is expected. If laboratory assessments are needed to follow-up unresolved adverse events, retrieval of assessments performed at a local institution close to the subject is acceptable.

The outcome of adverse events with a date of onset during the study period should be reevaluated. All serious adverse events, and those non-serious adverse events assessed by the investigator as possibly related to study drug should continue to be followed even after subject withdrawal from study. These adverse events should be followed until they resolve or until the investigator assesses them to be “chronic” or “stable.”

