10.1.1. Reporting Period

For each patient, the safety event reporting period begins at the time of the patient's first dose of Sunitinib or the time of the patient's informed consent if s/he is already exposed to Sunitinib, and lasts through the end of the observation period of the study, which must include at least 28 calendar days following the last administration of a drug under study; a report must be submitted to Pfizer Safety (or its designated representative) for any of the types of safety events listed in the table above occurring during this period. If a patient was administered a drug under study on the last day of the observation period, then the reporting period should be extended for 28 calendar days following the end of observation. Most often, the date of informed consent is the same as the date of enrollment. In some situations, there may be a lag between the dates of informed consent and enrollment. In these instances, if a patient provides informed consent but is never enrolled in the study (eg, patient changes his/her mind about participation, failed screening criteria), the reporting period ends on the date of the decision to not enroll the patient.

If the investigator becomes aware of a SAE occurring at any time after completion of the study and s/he considers the SAE to be related to sunitinib, the SAE also must be reported to Pfizer Safety.

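### Protocol 8.3.4 sets no earliest day for the closing adverse-event assessment, so a visit before day 28 complies and later adverse events may go unasked

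*Protocol*

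**What the plan says.** Four protocol sections bear on when AEs are assessed after sunitinib stops.

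- **Section 8.3.4** (post-treatment follow-up visit) lists "Assessment of adverse events within 28 days (+10 days) after the end of treatment or study withdrawal". The physical examination and laboratory items in the same list carry the same 28-day (+10) phrase.
- **Section 8.2.2** covers the subject who cannot attend that visit in person: "telephone contact with the subject to assess adverse events and concomitant medications and treatments is expected and is to be conducted at least 28 calendar", again with a 10-day allowance. Here 28 is a lower limit. The sentence does not say what the 28 days are counted from.
- **Section 10.1.1** defines the safety reporting period as running to the end of observation, "which must include at least 28 calendar days following the last administration of a drug under study". A report is required "for any of the types of safety events listed in the table above occurring during this period".
- **Section 8.1** describes a later stage that starts "After discontinuation of treatment and mandated 28 day follow-up"; it gathers data on new cancer treatment and survival.

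Section 8.3 adds that "there are no patient visits specified by virtue of this protocol". The frequency of AEs and serious AEs is the primary outcome (protocol 8.7, SAP 6.2).

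**The concern.** Section 8.3.4 is the only place where a post-dose AE assessment is scheduled, and it is worded as an upper limit. A site that sees the patient in clinic on day 7 has met it. A site that telephones the same patient under 8.2.2 must wait until day 28. The first patient has been asked about one week after the last dose and the second about four.

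Take a last dose on day 0, a clinic visit on day 7 and a non-serious event that starts on day 20. The telephone route asks about that event. The clinic route need not.

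Any resulting error runs one way, towards fewer recorded events, in the primary outcome of a study set up to meet a post-marketing safety commitment. Patients who stop because of toxicity are among those affected.

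**Working it through.** The plan states no figure that this point depends on, so there is none to reproduce. The check compares the sections and then does window arithmetic.

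**1. Does the phrase in 8.3.4 date the visit or the events?** Read alone, it could mean assessing AEs that occur in the 28 days. In the same list, however, the phrase is attached to the physical examination and the laboratory tests, where it can only say when the procedure is done. The visit-timing reading is the natural one. It allows any day up to 28 + 10 = 38 and names no first day.

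**2. Is another AE questioning scheduled after an early visit?**

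- Section 8.3.3 (safety data) is headed as running from first to last dose.
- Section 8.3.5 covers progression and survival.
- Section 8.3.4 provides a telephone contact only when the subject cannot return, not when the visit was early.
- Section 8.1.1 has patients questioned at each visit, but 8.3 fixes no visits.

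None is explicitly scheduled.

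**3. Days left unasked.** With day 0 as the last dose, unasked days = max(0, 28 − visit day).

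| Visit day | Unasked days | Share of 28 |
|---|---|---|
| 1 | 27 | 96% |
| 7 | 21 | 75% |
| 14 | 14 | 50% |
| 21 | 7 | 25% |
| 28 to 38 | 0 | 0% |

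**4. Upper bound on patients missed (illustration).** Let p be the true proportion of patients with a given AE by day 28 after the last dose, T the days on treatment and d the visit day. Assume a constant hazard, every patient seen on day d, and no later event ever captured. Then

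missed = p − [1 − (1 − p)^((T + d)/(T + 28))].

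The inputs p and T are assumptions. For T, 11.4 months is the Phase 3 median progression-free survival on sunitinib quoted in protocol section 6, used as a stand-in for a long treatment; 2 months stands for an early stop. With the SAP's 30.44 days per month, T = 347.0 and 60.9 days.

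Example with d = 7, T = 347.0 and p = 20%: the exponent is 354.0/375.0 = 0.944, the captured proportion is 1 − 0.8^0.944 = 19.0%, and 1.0 patient per 100 is missed.

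| Day-7 visit, patients missed per 100 | p = 5% | p = 20% | p = 50% |
|---|---|---|---|
| T = 11.4 months | 0.3 | 1.0 | 2.0 |
| T = 2 months | 1.2 | 4.3 | 8.9 |

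Under these assumptions the loss lies between zero and the value shown. A hazard that rises just after stopping would raise the bound; one that falls off drug would lower it.

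**The case against.** The case on the other side is substantial.

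- **The duty to record does not end with the visit.** Section 10.1 requires all AEs, serious or not, on the case report form. Section 10.1.1 keeps the reporting period open for at least 28 days after the last dose, whatever the visit day. A reader might infer that AE collection closes at an early visit. The documents do not support that.
- **The reduced follow-up starts later than the visit.** Under 8.1 it begins "After discontinuation of treatment and mandated 28 day follow-up", so a patient seen on day 7 is still inside the mandated period.
- **Later contacts may recover events.** Section 8.2.2 describes visits usually every 1 or 2 months, 8.1.1 has AEs asked about at each visit with an example question reaching back to the previous visit, and 8.3.5 continues follow-up for progression and survival.
- **The intention was probably day 28 to 38.** An allowance in the plus direction only, together with 8.1, 8.2.2 and 10.1.1, points that way.

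All of this stands, and it limits the consequence. It does not remove the gap in the wording. A duty to report takes effect once the site is aware of an event, and it does not make anyone ask. Serious AEs are the better protected, since they are likely to come to attention and must be reported within 24 hours of awareness. Non-serious AEs go only on the case report form, and many are known only by asking. If the intended window was day 28 to 38, the written window in 8.3.4 does not say so.

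**Conclusion.** Section 8.3.4 is inconsistent with 8.2.2, 8.1 and 10.1.1 on the earliest day of the closing AE assessment, and the sections need to be reconciled. As written, AEs that start after an early clinic visit may be under-recorded in the primary AE frequency, mainly non-serious events known only by asking.

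A reader might go further and conclude that the plan undercounts AEs, or might average the unasked share over all permitted visit days. The documents support neither. They give no distribution of visit days and no post-dose AE rate, and the reporting duty stays open.

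What can be stated firmly is the window arithmetic: 75%, 50% and 25% of the 28 days unasked for visits on days 7, 14 and 21. The effect on AE percentages cannot be derived. Under the assumptions above it is at most about 2 patients per 100 with long treatment, and larger for early stoppers. It is worth correcting because the outcome is primary, any error has one direction, and the remedy is cheap.

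**What to change.** Amend the AE bullet of protocol 8.3.4 only. State that the AE assessment takes place no earlier than 28 calendar days (+10 days) after the last dose, which matches the lower limit in 8.2.2 and takes its starting point from 10.1.1. Where the clinic visit falls before day 28, complete the assessment between day 28 and day 38 with the telephone contact already provided for in 8.2.2 and 8.3.4. For a subject who leaves the study, do the same unless consent for further data has also been withdrawn, since 8.2.2 and 9.2 then bar further collection.

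The examination and laboratory windows in 8.3.4 can stay. The abstract and SAP 2.1 need no change, because their 28-day phrase dates only the examination, laboratory and thyroid items.

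With this change none of the 28 days is left unasked in patients who can be reached. The cost is one wording amendment, one telephone contact for each patient seen early, and possibly a slightly higher recorded AE count.
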